2. Change from baseline to 12 weeks in systolic BP in the comparisons above. Between group change in hypertension status from baseline to 12 weeks. Worsening of hypertension at any time point will be defined either as an increase in BP medication or an increase in seated clinic diastolic BP of ≥ 10 mmHg or systolic BP ≥ 20 mmHg. Within-group change in hypertension status from 12w to 24 w will be compared to the control period of 0 to 12w in the delayed start group.
3. The primary outcome variable in this aim is to examine the change in FMD from baseline to 4 weeks in those treated with EPO compared to the waitlisted group. The hypothesis being tested is that EPO will cause impairment in endothelial function. Accordingly, those on EPO will have worsening of FMD.
4. The primary outcome variable in this aim is to examine the predictors of change in FMD from baseline to 4 w in those treated with EPO compared to time controls. Predictors of this change will be baseline values of the following variables: ADMA, urine nitrate and nitrite, renin, aldosterone, and plasma endothelin-1 and change from baseline to 4 w in the above variables. This analysis will answer the question: which of the pathways independently is predictive of endothelial dysfunction?

Sample Size

The primary objective of the study is to assess the change from baseline to 12 weeks in diastolic BP in EPO treated patients compared to controls. In the waitlisted group, we will measure the change from 12 weeks to 24 weeks compared to the change from 0 to 12 weeks. We have measured 24h

ambulatory BP in 183 CKD patients 4 weeks apart. The mean diastolic BP at baseline was 68.3 mmHg and at 4 weeks 68.1 mmHg. The mean difference was 0.14 mmHg and the standard deviation of the difference was 10.3 mmHg. With these assumptions, two-tailed tests and 80% power, the required sample size to detect a between-group difference of 5 mmHg is 68 subjects completing the study in each group. Assuming 85% of those randomized complete the trial, we would need to randomize $68/0.85 = 80$ subjects per group, or 160 subjects in total.

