- model 1: The outcome variable will be 24h ambulatory diastolic BP. The predictors will be indicator variables for group (early or late start), time (baseline and 12 weeks), stratum (UACR: none, high, very high) and all interactions. The random component of the mixed model will include subject and time. Unstructured covariance will be used with estimation of marginal means by maximum likelihood. We expect the interaction between group by time to be significant. The random coefficient analysis does not require baseline systolic BP as a covariate. If the 3-way interaction term (group x time x stratum) is significant, then results will be reported within each stratum. Confirmatory analyses will utilize change from baseline in clinic diastolic BP.
- model 2: The outcome variable will be 24h ambulatory diastolic BP. The predictors will be indicator variables for period within the delayed start group (early or late), time (baseline and 12 weeks from start of period), stratum (UACR: none, high, very high) and

all their interactions. The random component of the mixed model will include subject and time. We expect the interaction between period by time to be significant. If the 3-way interaction term is significant, then results will be reported within each stratum.

Accounting for missing data

Ambulatory BP recording, the gold-standard to assess BP, is carried out only twice during the trial in the parallel group analysis, but clinic BP measurements occur every 4 weeks. Patients who drop out but have some post-baseline measurements of clinic BP will be included in the analyses, thus minimizing loss to follow up. We will impute ambulatory BP as follows: we will use the complete data to build a model that relates the follow-up mean 24-hour ambulatory diastolic BP from the baseline 24-hour ambulatory diastolic BP and the clinic measures using repeated measures Mixed Model regression - then use the expected value from the model for the missing value - and use PROC MI (which generates maybe 5 replicate values to insert variability into the imputation) so that there is a price to pay for imputing.

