Comparison of the cohort with these measurements will also be done to understand if the inferences based on the ambulatory BPs accurately reflect the differences between the treatment groups using the clinic BPs. Repeated measures mixed models (PROC MIXED in SAS) will be utilized to assess the overall differences between the treatment groups using the clinic BPs. Additional analyses will explore the nocturnal patterns between the groups in the ambulatory BPs as well as the pattern over time using circadian models of BP in each group.

Between-group changes in hypertension status from baseline to 12 weeks will be tested using logistic regression. Worsening of hypertension at any time point will be defined either as an increase in BP medication or an increase in seated clinic diastolic BP of ≥ 10 mmHg or systolic BP ≥ 20 mmHg. The McNemar test will be used to compare within-group change in hypertension status from 12w to 24 w to that in the control period of 0 to 12w.

To test the hypothesis that EPO is causal to EIH via worsening of FMD, we will evaluate changes from baseline in FMD. That is, we will test if the worsening is a mediation effect using the technique described by Judd and Kenny⁹⁶ and elaborated by MacKinnon⁹⁷. The technique, expanded here for more than one potential mediator employs three regression equations:

- A. $Y = \beta_0 + \tau X_p + \varepsilon$
- B. $X_i = \beta_0 + \alpha_i X_p + \varepsilon$
- C. $Y = \beta_0 + \tau' X_p + \beta_1 X_1 + \dots + \beta_i X_i + \dots + \beta_k X_k + \varepsilon$ for all mediators together,
or $Y = \beta_0 + \tau' X_p + \beta_i X_i \varepsilon$ for each mediator separately

Y is the outcome result (e.g., change in 24-hour diastolic systolic BP), X_p is the group (early vs delayed start) and X_i represent the k purported mediators. The total effect of the treatment on the outcome (measured by the coefficient, τ) is the sum of direct effect (τ') of the treatment and the mediated, or indirect, effects ($\alpha_i \beta_i$). Mediation is established when four conclusions are met: (1) the treatment predicts the outcome variable (supported by a test of statistical significance of τ in equation [A]); (2) the treatment causes the potential mediator (α_i is significant in [B]); (3) the mediator causes the

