outcome variable controlling for the group assignment (β_i is significant in [C] and $\tau' < \tau$, which provides evidence for mediation rather than suppression); and (4) the mediated effect is statistically significant. For mediators that satisfy conclusions 1 through 3, the significance of mediation (conclusion 4) will be determined via interval estimation of the mediated effect using the asymptotic variance derivation of Sobel ⁹⁸ since the outcomes are the continuous measures. Additional analyses that look at thresholds of change (binary: worsening of hypertension or not) will utilize bootstrapping methods and logistic regression. The proportion of the effect mediated is calculated as the ratio of the indirect effect to the total effect, or $\alpha\beta/\tau$.

The primary outcome for flow-mediated dilatation is change in FMD from baseline to 4 w in those treated with EPO compared to time controls. Predictors of this change will be baseline values of the following biomarkers: plasma ADMA, urine nitrate and nitrite, and plasma renin, aldosterone, and endothelin-1 and change from baseline to 4 w in the above biomarkers. In addition, the baseline FMD will be an independent variable. This analysis will use regression models similar to the above-listed analyses.

Pre-specified sub-group analyses for BP response

- Effect of age: The effect of age (e.g., 65 or more and <65) will be tested using interaction effects.
- Effect of volume overload: Volume overloaded subjects are more likely to show worsening EIH with EPO therapy. In people with volume overload, renin and aldosterone levels are expected to be low and 24-hour urine Na high. We will dichotomize the baseline levels of these markers and examine the outcome on ambulatory BP using interaction effects.

Safety analysis

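### The ambulatory BP imputation model omits FMD and treatment group, and the mediation equations have no defined common patient set

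*Combined protocol and SAP*

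**What the plan says.** Under Accounting for missing data, only ambulatory BP is imputed. The model predicts follow-up 24-hour diastolic BP "from the baseline 24-hour ambulatory diastolic BP and the clinic measures". Neither FMD nor treatment group is listed as a predictor, and no rule is given for missing FMD or biomarkers. On who is kept, the section says: "Patients who drop out but have some post-baseline measurements of clinic BP will be included in the analyses".

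The mediation text follows under the same heading. Equation A regresses the change in 24-hour BP on group, B regresses each mediator on group, and C regresses the BP change on group and mediators. The total effect τ is described as the sum of the direct effect τ' and the indirect effects αβ. "Mediation is established when four conclusions are met". The third requires a significant β and τ' < τ, "which provides evidence for mediation rather than suppression". Finally, "The proportion of the effect mediated is calculated as the ratio of the indirect effect to the total effect".

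The plan does not say which patients enter A, B or C, or whether imputed ambulatory BP is used there.

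**The concern.** There are two separate weaknesses.

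**Imputation model.** Values drawn from a model without FMD carry only as much of the FMD-BP association as clinic BP happens to transmit. Mixing them with observed values biases β, and so αβ, toward zero. Leaving out treatment group does the same to τ.

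**Patient set.** The relation τ = τ' + αβ is exact in linear regression only when all equations use the same patients. Equation A needs no FMD, whereas B and C do. With no set defined, regression software keeps a patient without FMD in A and drops that patient from B and C. The τ' < τ check and the ratio αβ/τ then compare different groups of patients.

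At stake is the estimate of how much of the BP effect runs through endothelial function, which is the mechanism the trial was designed to study.

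**Working it through.** **Inputs from the plan (Sample Size).** For the change in diastolic BP, "the standard deviation of the difference was 10.3 mmHg". Further, "the required sample size to detect a between-group difference of 5 mmHg is 68 subjects completing the study in each group", with "two-tailed tests and 80% power". The SD of FMD change is 0.93%, the detectable FMD change 0.45%, and 85% are assumed to complete.

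**Reproducing the plan's figure.** With two-sided alpha 0.05 (not stated), n = 2(1.96 + 0.84)² × 10.3² / 5² ≈ 67 per group. The t-based solution is 67.6, rounded up to 68, and 68/0.85 = 80. The stated sample size is confirmed. The plan gives no figure for the mediation analysis or for missing FMD.

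**Assumed.** 80 per arm; τ = 5; group effect on FMD −0.45; true indirect effect 1.5 mmHg (proportion 0.30), so β = 1.5/(−0.45) = −3.33; share of ambulatory BP imputed f = 0.15, missing at random; correlation of clinic with ambulatory BP ρ = 0.5; five imputations.

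**Step 1: FMD omitted.** An imputed value keeps about ρ² of the FMD-BP covariance. The retained share of β and αβ is therefore 1 − f(1 − ρ²).

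- f = 0.15, ρ = 0.5: 1 − 0.15 × 0.75 = 0.888, a loss of 11%; αβ = 1.5 × 0.888 = 1.33. Simulation gives 1.31-1.33.
- ρ = 0.3: 1 − 0.15 × 0.91 = 0.864, a loss of 14%.
- ρ = 0.7: 1 − 0.15 × 0.51 = 0.924, a loss of 8%.
- f = 0.05, ρ = 0.5: 1 − 0.05 × 0.75 = 0.963, a loss of 4%.

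**Step 2: group omitted.** The same factor applies approximately to τ: 5 × 0.888 = 4.44. Simulation gives about 4.4.

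**Step 3: proportion mediated (f = 0.15, ρ = 0.5).**

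| Imputation model | τ | αβ | αβ/τ |
|---|---|---|---|
| As written (no group, no FMD) | 4.41 | 1.33 | 0.30 |
| Group added, FMD omitted | about 5.0 | 1.32 | 0.26 |
| Group and FMD added | 4.97 | 1.50 | 0.30 |

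As written, numerator and denominator shrink together, so the ratio looks right while both effects are too small. Adding group alone corrects τ but exposes the bias in αβ.

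**Step 4: different patients.** If A uses 80 per arm and C only the n_s per arm with FMD, the chance gap in τ has SD 10.3 × √(2/n_s − 2/80):

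- 5% missing FMD, n_s = 76: 0.37 mmHg
- 10%, n_s = 72: 0.54 mmHg
- 15%, n_s = 68: 0.68 mmHg

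On one common set the gap is 0.000 in every run, even when the imputation omits FMD and group. The two weaknesses are therefore independent of each other.

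**Step 5: effect on the decision.** Under the full four-part rule, with FMD missing at random and BP complete, the chance of declaring mediation was as follows.

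| True indirect effect | Missing FMD | A on all patients | A on FMD subset |
|---|---|---|---|
| 0.9 mmHg | 10% | 23.2% | 22.5% |
| 0.9 mmHg | 20% | 18.0% | 17.1% |
| 0.5 mmHg | 10% | 6.1% | 6.0% |
| 0.5 mmHg | 20% | 5.2% | 4.7% |

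With no mediation it was about 0.5% either way.

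**The case against.** The best defence is that the plan never commits to the faulty procedure. It does not say that imputed ambulatory BP enters the mediation analysis, and a statistician could fit A, B and C to one set without departing from any sentence. That stands: the patient-set problem is an omission. A reader might infer that the plan runs A and C on different patients, but the documents name no set, so they do not support that reading.

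Timing also limits the mismatch. Imputation needs a post-baseline clinic BP. The first is at week 4 (Overall trial design and plan, Figure 2), the visit at which FMD is scheduled. Someone who leaves earlier has neither measurement; someone who leaves later should have both. Only a failed or missed scan, or an unusable baseline scan, creates a mismatch. This is possible without dropout, because FMD needs fasting and clear arterial images while clinic BP does not. The rate is not given, and the 15% non-completion figure is not a missing-FMD rate.

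A reader might also infer that the mediation verdict would often turn on who is missing. With a true indirect effect of 0.9 mmHg and 10-20% of FMD missing at random, τ' ≥ τ alone occurs in 11-18% of simulated trials. But the plan never uses that inequality alone, and Step 5 shows that the full rule hardly moves. Under random missingness the mismatch also leaves the average ratio unshifted. If FMD were missing mainly in treated patients whose BP rises, an added assumption, 10% missing would put the identity off by 1.36 mmHg on average and move the ratio from 0.30 to 0.26.

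The attenuation is modest against sampling error. With β about −2 (an indirect effect of 0.9 mmHg) and a standard error of about 0.86, an 11% loss is 0.22/0.86, or about a quarter of a standard error. It is nonetheless a systematic bias that a better imputation model removes.

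**Conclusion.** The imputation point holds, provided that the imputed values are used for mediation. With 15% imputed and ρ = 0.5, β and αβ are about 11-12% too small, and τ falls from 5.0 to about 4.4-4.5 mmHg. Adding group without FMD turns a true proportion of 0.30 into about 0.26. The loss in αβ is about 8% to 14% for ρ from 0.7 to 0.3, and about 4% if only 5% of values are imputed. The missing group term would also affect the primary BP comparison if imputed values are used there.

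The patient-set point holds as an omission. Its size rests on a missing-FMD rate that the documents do not give, and under random missingness its effect on the four-part decision is small.

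A reader might link the two and conclude that leaving FMD out of the imputation is what breaks τ = τ' + αβ. It is not: on a common set the identity is exact whatever imputation model is used.

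**What to change.** In the PROC MI model, add treatment group, UACR stratum, and baseline and week-4 FMD to ambulatory and clinic BP. Add the other mediators whenever they are analysed. Fit A, B and C to the same patients in each completed data set, and state how missing FMD and biomarkers are handled. As a minimum, restrict all three equations to patients with both FMD measurements and a diastolic BP change.

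The cost is some SAP wording and programming; no new patients, visits or measurements are needed. The minimum option makes equation A slightly less precise.

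### The imputation model for missing week-12 ambulatory diastolic BP does not name treatment arm, so imputed patients receive only the part of the EPO effect that clinic BP carries

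*Combined protocol and SAP*

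**What the plan says.** Under Primary Analysis, model 1 analyses 24-hour ambulatory diastolic BP with "indicator variables for group (early or late start), time (baseline and 12 weeks), stratum (UACR: none, high, very high) and all interactions". The group-by-time term carries the primary hypothesis. The plan adds: "If the 3-way interaction term (group x time x stratum) is significant, then results will be reported within each stratum".

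Under Accounting for missing data, "Patients who drop out but have some post-baseline measurements of clinic BP will be included in the analyses". Their missing ambulatory value comes from a model fitted to the complete data that "relates the follow-up mean 24-hour ambulatory diastolic BP from the baseline 24-hour ambulatory diastolic BP and the clinic measures". The analyst is to "then use the expected value from the model for the missing value" and also to "use PROC MI (which generates maybe 5 replicate values to insert variability into the imputation", "so that there is a price to pay for imputing".

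The same section later describes mixed models that "will be utilized to assess the overall differences between the treatment groups using the clinic BPs". That is a separate analysis of clinic BP, not the imputation model. No section adds arm or stratum to the imputation, or says that imputation is done separately by arm.

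**The concern.** An imputation model should contain the variables that the analysis model tests. If arm is left out, a patient on EPO and a waitlisted patient with the same baseline ambulatory BP and the same clinic readings get the same predicted week-12 value. Any part of the EPO effect that clinic BP does not show is then missing from the imputed values, and the group difference is pulled toward zero.

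The objectives say that the study should quantify precisely how far BP rises. Under the present rule, the effect credited to patients without a week-12 recording depends on how well clinic BP happens to predict ambulatory BP. It is not an assumption that anyone has stated and can defend.

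**Working it through.** **Inputs from the plan (Sample Size).** Difference 5 mmHg, SD of change 10.3 mmHg, two-tailed test, 80% power, 85% completing, 80 randomized per group. Alpha is not stated there; I take 0.05.

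**The plan's own figure.** The normal formula gives n = 2 x (1.960 + 0.842)² x 10.3² / 5² = 66.6, or 67 per group. The t-based version gives 67.6, or 68. Then 68 / 0.85 = 80. The sample size reproduces.

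**Attenuation.** Assume that missingness is unrelated to outcome, is equal in the two arms, and that dropouts keep their arm's effect. Observed patients (share 1 - d) contribute the full difference. Imputed patients (share d) contribute c times it:

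estimate = 5 x [(1 - d) + d x c] = 5 x [1 - d(1 - c)]

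| d | c | Estimate (mmHg) | Loss |
|---|---|---|---|
| 15% | 0 | 5 x 0.85 = 4.25 | 15% |
| 15% | 0.5 | 5 x 0.925 = 4.63 | 7.5% |
| 15% | 1 | 5.00 | 0% |
| 10% | 0 | 4.50 | 10% |
| 5% | 0 | 4.75 | 5% |

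**What c might be.** The documents do not give it, so these figures are illustrations only. Assumptions: ambulatory SD 11, clinic error SD 7, and a clinic response equal to the ambulatory one that builds linearly to week 12. I took c from the large-sample coefficients of the pooled regression without arm, with d = 15%. The result depends on how an individual patient's BP is assumed to move between visits:

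| Patient path | c, last clinic BP at week 4 / 8 / 12 | Estimate (mmHg) |
|---|---|---|
| Straight line from baseline to week 12 | 0.17 / 0.50 / 0.74 | 4.38 / 4.63 / 4.80 |
| Equal correlation across visits | 0.08 / 0.20 / 0.69 | 4.31 / 4.40 / 4.77 |
| Autoregressive | 0.11 / 0.35 / 0.70 | 4.33 / 4.51 / 4.78 |

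With clinic error SD from 4 to 10, the three paths together give about 4.3 to 4.9 mmHg.

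**Inference.** Simulation used 80 per arm, 15% missing completely at random, five imputations and 4,000 or more replicates. At c = 0 with clinic BP to week 4:
- without arm: mean estimate 4.27 mmHg, mean SE 1.75, coverage 0.952, power 0.70
- with arm: 5.03 mmHg, SE 1.74, coverage 0.949, power 0.82
- no imputation: 5.03 mmHg, SE 1.76, coverage 0.954, power 0.81

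The bias at c = 0 is therefore 0.75 / 1.75 = 0.43 of a standard error. Under no true effect, rejection with arm omitted was 0.030 to 0.043.

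**Stratum.** Because randomization is within UACR stratum, omitting stratum does not bias the overall difference. The stratum-specific results do suffer, and the missing piece is arm by stratum. With assumed stratum effects of 2.5, 5 and 7.5 mmHg, the true high-minus-low contrast is 5. The estimates were 4.10 to 4.83 with arm only, 4.12 to 4.86 with stratum main effects added, and 4.86 to 5.07 with arm by stratum.

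**The case against.** **The plan is silent; it does not exclude arm.** The sentence is informal, and a statistician might add arm unprompted. That is fair, but a pre-specified rule for the primary endpoint should not depend on it.

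**15% is an unlikely case.** A reader might infer that the primary result will come out 15% too small. The documents do not support that. The loss needs every non-completer to be imputed and clinic BP to carry none of the effect, yet the plan uses clinic diastolic BP as its confirmatory outcome. The 85% refers to completing the trial, which lasts 24 weeks in the delayed-start arm. Patients with no post-baseline clinic BP are not clearly imputed, and those who stop the drug remain under study. So d may be below 15%. Nor is 15% a strict upper limit: with an assumed clinic effect of -2.5 mmHg, opposite to the ambulatory effect, simulated losses were 17% to 20% when clinic and ambulatory residuals were correlated (0.3 to 0.7). A clinic effect well above the ambulatory one can remove or slightly reverse the bias.

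**The target matters.** This is the strongest objection. The safety section invokes intention to treat. If patients with missing recordings lose the effect entirely, the target at 15% is 0.85 x 5 = 4.25 mmHg. In simulation the rule as written then gave 4.28 to 4.67, and imputation with arm gave 5.00 to 5.06. So the estimate is too small only if dropouts keep their arm's effect. The present rule would come near the other target only by accident of c, which is why the assumption has to be stated and varied.

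**Clinic BP is analysed separately.** That is a useful cross-check, but it does not correct the ambulatory estimate.

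**Conclusion.** The concern holds in limited form. Followed as written, the rule changes the estimated difference by the factor 1 - d(1 - c). At 15% imputed, that is 4.25 mmHg at c = 0, 4.63 at c = 0.5 and no loss at c = 1. The result assumes missingness unrelated to outcome, similar missingness by arm, and dropouts who keep their arm's effect. The documents do not give c, so the expected loss cannot be fixed; 4.3 to 4.9 mmHg is an illustration under stated assumptions.

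A reader might also infer that the primary test is invalid. It is not: type I error is not inflated, simulated coverage stayed at 0.93 to 0.97, and the bias at c = 0 is about 0.43 of a standard error, mainly against the trial's own hypothesis. Power falls below that of no imputation only when clinic BP carries little of the effect. This is a cheap improvement, not a flaw that undermines the trial.

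**What to change.** Replace the imputation sentence with wording such as: missing week-12 ambulatory diastolic BP will be multiply imputed with PROC MI from a model containing treatment arm, UACR stratum, arm by stratum, baseline ambulatory diastolic BP and all available clinic diastolic BPs; the number of imputations is fixed in advance; results are pooled by Rubin's rules. Arm by stratum is needed only so that the three-way term and the stratum-specific results are not diluted.

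Delete the instruction to use the expected value. The stated purpose already points to PROC MI draws. If arm were added while single expected values were analysed as observed data, simulated null rejection rose to as much as 0.079.

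State that the main analysis assumes data missing at random and that patients with missing recordings keep their arm's effect. Add a sensitivity analysis that subtracts a fixed amount from imputed EPO-arm values, over a range chosen by the sponsor. At 15% imputed, each 1 mmHg subtracted lowers the estimate by 0.15 mmHg.

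**Cost.** SAP wording only: no patients, visits or measurements are added. Simulated power with arm included was 0.81 to 0.85, against 0.79 to 0.81 with no imputation. The downside is that imputing with arm credits dropouts with the full effect. If they lose it, the intention-to-treat difference is overstated by up to 0.15 x 5 = 0.75 mmHg at 15% imputed. The sensitivity analysis is therefore part of the fix.

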Harms will be assessed by monitoring changes in weight, eGFR, CBC, clinic BP, and ABPM. For more definitive assessments, including hospitalizations, serious adverse events will be properly completed and sent to the VAMC DMC as requested. Safety of continued participation will be assessed at each study visit. The stop-points will be treatment-emergent severe adverse events that precludes further exposure to the drug, such as an allergic drug reaction, initiation of renal replacement therapy, or death. If the study drug is stopped, the subject will be continued to be studied so as to not violate the intention-to-treat principle.

Participants

Inclusion Criteria

- Stage 3 or 4 CKD defined as eGFR <60mL/min/1.73m² for ≥3 months or persistent albuminuria for ≥3 months; (i) urine albumin to creatinine ratio of more than 30 mg/g; (ii) urine protein to creatinine ratio of more than 150 mg/g; or (iii) at least 1+ dipstick positive proteinuria. ⁸⁸
- 24h ABPM <140/90 mmHg at baseline in the presence or absence of antihypertensive treatment.
- Hgb between 8 and 10 g/dL.
- No treatment with ESA within the previous 3 months.
- Adults, age 18 and older.

Exclusion Criteria

- Need for packed RBC transfusion in the previous 2 months.
- Myocardial infarction, stroke, or hospitalization for heart failure in the past 2 months.
- In the assessment of the investigator, have hematologic, inflammatory, infectious, or other conditions that might interfere with the erythropoietic response.

Retention of Participants

For half of the participants, only 7 visits are needed. For the others, at least 11 visits over 24 weeks of the trial are needed. We will offer \$20 per visit for participation in the trial to offset travel and time costs.

METHODS

Method of Randomization

Participants will be randomized in a 1:1 ratio to either early or delayed treatment (“waitlisted group”) with EPO according to UACR strata. A random permuted block design will be used to avoid imbalance in assignment to the treatment groups over time. A randomization sequence will be generated by the statistician and individually concealed in sequentially numbered opaque envelopes. After confirming eligibility with the principal investigator, the study pharmacist will dispense EPO according to the randomization sequence.

Measurement of clinic BP

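### Missing week-12 ambulatory BP: the plan names two different imputation methods without saying which feeds model 1, leaves the number of imputations open, and omits treatment group from the imputation predictors

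*Combined protocol and SAP*

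**What the plan says.** The primary outcome is 24-hour ambulatory diastolic BP. Under Primary Analysis, model 1 compares the groups at baseline and 12 weeks in a mixed model: "Unstructured covariance will be used with estimation of marginal means by maximum likelihood".

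The section Accounting for missing data then says "Patients who drop out but have some post-baseline measurements of clinic BP will be included in the analyses". It has the analyst relate follow-up ambulatory diastolic BP to baseline ambulatory diastolic BP and the clinic measures in the complete data, "then use the expected value from the model for the missing value - and use PROC MI (which generates maybe 5 replicate values". The rest of the sentence gives the purpose: the replicates add variability so that imputing carries a cost.

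The section does not say:
- whether the expected value or the PROC MI draws are analysed in model 1;
- how many imputations will be made, with what seed, and how results are pooled;
- whether treatment group or UACR stratum is in the imputation model (neither is listed);
- whether the imputed analysis or maximum likelihood on the observed data gives the primary p-value.

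On the likely amount of missing data, Sample Size says "Assuming 85% of those randomized complete the trial".

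**The concern.** Inserting a model's expected value is deterministic single imputation. It leaves out residual and parameter uncertainty, and the analysis then counts the imputed patients as observed. Multiple imputation draws random values and needs no expected-value step. Two competent programmers could read the sentence differently, report different results for the same data, and both claim to have followed the plan.

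Three things are at stake:
- the calibration of the test, if expected values are analysed;
- the reproducibility of a borderline p-value, if a handful of unseeded draws is used;
- the size of the estimated effect, if the imputation model does not know which arm a patient is in.

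**Working it through.** **Inputs from the documents.** SD of change: "the standard deviation of the difference was 10.3 mmHg". Difference to detect: 5 mmHg. Test and power: "With these assumptions, two-tailed tests and 80% power". Allocation: 1:1. Completion: 85%.

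**Assumptions not in the documents.** Alpha 0.05; baseline to week-12 ambulatory correlation 0.6; correlation r of clinic BP with follow-up ambulatory BP, given baseline, of 0.3, 0.5 or 0.7; data missing completely at random; strata ignored.

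**The plan's own figure.** The normal approximation gives 2 × (1.96 + 0.84)² × 10.3² / 5² = 66.5, so 67 per arm. The t-based calculation gives 68 (power 0.802 at 68, 0.797 at 67). Then 68/0.85 = 80 per arm. The sample size is reproduced and is not in dispute. The 15% loss is 80 × 0.15 = 12 patients per arm.

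**Reading 1: expected values analysed, group in the imputation model.** Let R² be the share of the variance of change that the imputation model explains. Baseline alone explains (1 − 0.6)/2 = 0.20, so R² = 1 − 0.8 × (1 − r²).

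Reported SE / true SE = √{[(1 − 0.15(1 − R²))/80] / [R²/80 + (1 − R²)/68]}

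| r | R² | SE ratio | Type I error, 2 × [1 − Φ(1.96 × ratio)] |
|---|---|---|---|
| 0.3 | 0.272 | √(0.01114/0.01411) = 0.89 | 8.2% |
| 0.5 | 0.400 | √(0.01138/0.01382) = 0.91 | 7.5% |
| 0.7 | 0.592 | √(0.01174/0.01340) = 0.94 | 6.7% |

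Simulation agrees within its error. In 3,000 null trials per setting, the reported SE was 1.53 to 1.58 mmHg against a true 1.70 to 1.72, with type I error 7.0% to 7.2%. A separate simulation gave an SE 8-11% too small and type I error 7.3% to 8.2%. The reported SE is even below 10.3 × √(2/80) = 1.63, the value had all 160 patients been measured. Type I error is 5.8% to 7.3% at 10% missing and 7.9% to 10.6% at 25%.

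**Reading 1 with only the listed predictors.** At 15% missing, simulated type I error was 4.8% to 5.6%, with reported SE 1.53 to 1.58 against true SE 1.52 to 1.61. Without group, the imputed patients add little of their own to the contrast between arms, so the estimate varies less and the small SE happens to match it.

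**Reading 2: PROC MI draws pooled by Rubin's rules, group included.** With 5 imputations, type I error was 4.2% to 5.4% in all nine combinations of missing share (10%, 15%, 25%) and r. The SE is valid. What remains is dependence on the seed: the SD of z between seeds is about √(FMI/m), where FMI is the fraction of missing information and m the number of imputations. FMI was 0.07 to 0.10 at 15% missing.

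- m = 5: √(0.07/5) = 0.12 to √(0.10/5) = 0.14.
- m = 50: √(0.07/50) = 0.04 to √(0.10/50) = 0.04.

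Data sets set to p = 0.05 (at m = 1000) were re-imputed with 400 seeds. The 5th to 95th percentiles of p were:

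| r | m = 5 | m = 50 | m = 100 |
|---|---|---|---|
| 0.3 | 0.029-0.097 | 0.043-0.061 | 0.045-0.058 |
| 0.7 | 0.032-0.087 | 0.045-0.060 | 0.046-0.057 |

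**Leaving group out, either reading.** If the predictors carried no information on the treatment effect, the imputed 15% would contribute no difference, and a true 5 mmHg would be estimated at 0.85 × 5 = 4.25. Clinic BP carries part of the effect, so the simulated estimates were 4.34, 4.40 and 4.64 mmHg for r = 0.3, 0.5 and 0.7, against 4.95 to 5.02 with group included. Another simulation gave 4.5 to 4.7. Multiple imputation without group is also conservative: type I error about 2-3%, closer to nominal as clinic BP becomes more predictive.

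**The case against.** The strongest reply is that the sentence describes one procedure: fit a prediction model, then let PROC MI put variability around its predictions. The purpose clause supports this, and on that reading even 5 imputations give a valid test. This makes multiple imputation the likelier intention. It does not remove the expected-value instruction, and it supplies neither the number of imputations, the seed nor the pooling rule.

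A reader might infer that the plan as written inflates type I error, perhaps to 10%. The documents do not support that. Inflation needs group in the imputation model, and the listed predictors do not include it. A figure near 10% at 15% missing needs R² = 0 (ratio √0.7225 = 0.85), although baseline ambulatory BP is a predictor. A reader might also add the two harms together. They are alternatives: expected values do not depend on a seed, and pooled draws do not understate the SE.

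Two further objections stand in part. Model 1 by maximum likelihood can use patients with only a baseline value, so it is an inference that imputed data produce the primary p-value. And 15% is assumed non-completion; only dropouts with a post-baseline clinic BP are brought in, so the imputed share may be smaller.

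Seed dependence matters only for borderline results. A pre-set seed alone makes the analysis repeatable, and more imputations narrow the range without removing it. The choice of 50 is therefore partly judgement.

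**Conclusion.** The point holds in conditional form. The plan gives two instructions for the same missing value and does not say which one model 1 uses.

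- **Expected values analysed, group in the imputation model:** SE about 8-11% too small and type I error about 7-8% (by the formula, slightly less when clinic BP is strongly predictive).
- **Expected values analysed, listed predictors only:** type I error near 5%.
- **PROC MI pooled, group included:** valid SE at m = 5, but p = 0.05 can print as roughly 0.03 to 0.10, against about 0.043 to 0.061 at m = 50.
- **Group omitted, either method:** a true 5 mmHg difference shrinks to about 4.3-4.6 mmHg, and multiple imputation becomes conservative.

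All sizes rest on the assumptions listed with the calculation, chiefly 15% missing completely at random and a correlation of 0.6. The bias toward no effect is the consequence closest to the text, because it follows from the predictors actually listed, provided that list is meant to be complete. This should be settled before the data are analysed; it does not call the design or the sample size into question.

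**What to change.** Delete the expected-value step and state one procedure:

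1. Impute with PROC MI draws that carry parameter and residual uncertainty, from a model with treatment group, UACR stratum, baseline ambulatory BP and clinic BP.
2. Set m = 50 and fix the seed in advance.
3. Fit model 1 in each completed data set and pool by Rubin's rules (PROC MIANALYZE).
4. State whether this analysis or maximum likelihood on the observed data gives the primary p-value.

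The cost is a few lines of SAP wording and some computing time. With group in the model, the SE will be larger than under the expected-value step, which is the cost of imputing that the plan says it wants.
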